Tau PET will be performed in a subset of participants at selected sites with access to the Sponsor-approved tau PET radiotracer(s). A Screening tau PET scan is mandatory for all participants at sites with tau PET scanning capabilities; a historical tau PET scan will not be accepted. Screening tau PET will not contribute to eligibility determination. The tau PET scan should only be performed at Screening Visit 3 after the participant has confirmation of a positive amyloid result (either PET or CSF) from Screening Visits 1 or 2, and after meeting all other eligibility criteria, including MRI criteria, at Screening Visits 1 and 2. Screening tau PET scan should be performed prior to randomization. Only in the event of inadequate radiotracer supplies or PET camera availability can the Screening tau PET scan be performed after Day 1, with Sponsor approval; the scan should be performed as close to the first infusion date as possible and must occur prior to the second infusion. The Screening Period may be extended up to 90 days in the event of logistical issues related to PET scans and/or due to other major causes (i.e., institutional restrictions or participant disposition due to COVID-19 or other major disasters/disruptions) and is subject to Sponsor approval. For all women of childbearing potential, a pregnancy test must be performed within 24 hours prior to every PET scan.

Brain MRI (Screening Visit 2) will not be performed until the participant has met the eligibility criteria and has acceptable laboratory tests from Screening Visit 1.

Safety FU telephone contacts occur during dose escalation. These FU contacts may be performed in person if the participant will be at the site for clinical assessments.

The Research Diagnostic Verification Form is used at Screening Visit 1 for initial diagnosis, and the Diagnostic Staging Form is used at subsequent visits to help standardize diagnostic change across the study. These forms should be completed after the CDR is performed (see the Study Reference Guide).

The baseline ADAS-Cog13 and the ADCS-ADL-MCI must be performed within 20 days of Screening Visit 1, but not on the same day as the screening of CDR or MMSE. These scales can also be performed on Day 1 prior to randomization and study treatment infusion.

The NPI-10 must be performed after the CDR but can be performed at any time during Screening or on Day 1.

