Table 3: Abbreviated Schedule of Activities for Participants Who Discontinue Study Treatment but Remain in the Study

Study Week 	12	24	40	50/52	64	78	88	104	106	_	UV for
Study Day	85 ± 3	169 ± 3	281 ± 3	351 ± 3	449± 3	547 ± 3	617 ± 3	729/743 ± 3	743 ± 3	ET 	ARIA 
Physical Examination		X	X	X	X		X	X		X	
Neurological Examination		X	X	X	X		X	X		X	
12-Lead ECG				X				X		X	
Vital Signs	X	X	X	X	X		X	X		X	X
Hematology, Blood Chemistry, and Urinalysis				X				X		X	
Urine Pregnancy Test 	X	X	X	X	X		X	X			
Coagulation Panel 				X		X		X		X	
CSF Collection 				X		X		X		X	
Amyloid PET 						X					
Tau PET 						X					
Brain MRI								X		X	X
		Clin	ical Scales,	Patient-Repo	orted Outcon	ies, QoL, and	HEOR Mea	sures			
Diagnostic Verification Form				X		X			X	X	
MMSE				X		X			X	X	
CDR				X		X			X	X	
ADAS-Cog13				X		X			X	X	
ADCS-ADL-MCI				X		X			X	X	
NPI-10				X		X			X	X	
C-SSRS-SLV	X	X	X	X	X	X	X	X	X	X	X

Study Week 	12	24	40	50/52	64	78	88	104	106	БТ 2	UV for	
Study Day	85 ± 3	169 ± 3	281 ± 3	351 ± 3	449± 3	547 ± 3	617 ± 3	729/743 ± 3	743 ± 3	ET 	ARIA 	
RUD-Lite				X		X			X	X		
QoL-AD 				X		X			X	X		
				Routi	ne Safety Mo	nitoring						
Concomitant Therapy and Procedures		Monitor and record continuously throughout the study										
AE Reporting		Monitor and record continuously throughout the study 										
SAE Reporting	Monitor and record continuously throughout the study 											

<sup>1 Participants who discontinue study treatment and withdraw from the study prematurely will attend an ET visit, and additionally a FU Visit, 18 weeks after their final dose, as noted in Table 2. Participants who discontinue treatment but agree to stay in the study will follow the abbreviated visit schedule outlined here. Participants will begin this Schedule of Activities at the visit that most closely follows study treatment discontinuation.

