# 5.2. Study Duration for Participants

The total duration of the study for each participant will be approximately 130 weeks, including a series of screening visits within 8 weeks before administration of the first dose, and a 104-week placebo-controlled treatment period. Additionally, participants will undergo a safety FU Visit 18 weeks after the final dose of aducanumab.

Participants will have approximately 39 scheduled clinic visits, 27 of which are dosing visits, as well as up to 8 telephone safety FU contacts, as follows:

- Screening Visits 1 to 3 will occur no more than 60 days before the first dose of study treatment on Day 1. Visits will be conducted on multiple days. All screening procedures should be completed within 60 days; however, with Sponsor approval, the overall screening period may be extended up to 90 days in the event of logistical issues related to PET scans (and/or due to other major causes [i.e., institutional restrictions or participant disposition due to COVID-19 or other major disasters/disruptions]). These screening visits will include baseline brain MRI, clinical scales of cognition and function, biological fluid sampling (including CSF), amyloid and tau PET scans (where available), physical and neurological examinations, and all other safety and efficacy assessments. See Section 1.3 for the Schedules of Activities.
- Twenty-seven dosing visits (Day 1 and Weeks 4, 8, 12, 16, 20, 24, 28, 32, 36, 40, 44, 48, 52, 56, 60, 64, 68, 72, 76, 80, 84, 88, 92, 96, 100, and 104).

- Eight telephone safety FU contacts after each of the first 8 doses.
- Four visits separate from dosing for clinical functional and cognitive assessments (Weeks 26, 50, 78, and 106).
- One safety FU visit at Week 122, 18 weeks after the last dose at Week 104, or 18 weeks after administration of the last dose for participants who discontinue treatment early.
- A minimum of 6 MRI visits, with 4 during treatment (Week 14 [before escalation to 6 mg/kg, before at the fifth dose], Week 22 [before escalation to 10 mg/kg, before the seventh dose], Week 30 [before the third dose at 10mg/kg], and Week 42 [before the sixth dose at 10 mg/kg]. Two additional MRIs will be performed at Week 106 and at Week 122 [EOS] 18 weeks after the final-dose safety FU) or 18 weeks after administration of the last dose for participants who discontinue treatment early.

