# 8. DISCONTINUATION OF STUDY TREATMENT AND/OR WITHDRAWAL OF PARTICIPANTS FROM THE STUDY

# 8.1. Discontinuation of Study Treatment

A participant *must* permanently discontinue aducanumab for any of the following reasons:

- The participant develops any new acute or subacute hemorrhage.
- The participant develops any treatment-emergent incident of cerebral hemorrhage > 1 cm in diameter on T2\* sequence.
- The participant develops a radiographically severe ARIA-H (10 or more treatmentemergent microhemorrhage or more than 2 treatment-emergent superficial siderosis)
- The participant develops any radiographic type of ARIA- E or ARIA-H accompanied by serious symptoms (according to the definition of serious adverse events in Section 11.1.2).
- The participant develops a cortical infarct (defined as > 1.5 cm in diameter irrespective of anatomic location).
- The participant develops more than 1 > 1 lacunar infarct (defined as  $\leq 1.5$  cm in diameter).
- The participant withdraws consent to continue study treatment.
- The participant experiences a medical emergency that necessitates permanent discontinuation of study treatment or unblinding of the participant's treatment assignment.
- The participant experiences an AE that necessitates treatment discontinuation or requires continued treatment that meets exclusionary criteria.
- The participant experiences a severe infusion reaction.
- The participant initiates treatment of Alzheimer's disease with a commercially available disease-modifying drug.
- At the discretion of the Investigator for medical reasons, including treatment-emergent ARIA events.
- At the discretion of the Sponsor for safety or other reasons.
- At the discretion of the Investigator or Sponsor for noncompliance.
- The participant becomes pregnant; study treatment must be discontinued immediately, and pregnancy must be reported according to protocol instructions.

The primary reason for discontinuation of study treatment must be recorded in the participant's CRF.

Participants who discontinue treatment are encouraged to remain in the study, attend a safety FU Visit 18 weeks after the last dose of study treatment, and immediately continue protocol required tests and assessments at a subset of the clinic visits (see Table 3) until the end of the study per the Schedule of Activities or until the participant withdraws consent.

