# 11.4. Procedures for Handling Special Situations

#### 11.4.1. Public Health Emergencies

In the event of a public health emergency that results in site closure, travel restrictions, and/or the study being deprioritized at the site such that clinic visit(s) cannot occur, a protocol deviation would be incurred for any deviation from the protocol-specified visits and assessments, with additional notation that this protocol deviation is due to the public health emergency.

If a protocol-specified clinical visit cannot occur due to a public health emergency, the following mitigating options should be pursued, in order of preference (in which the highest preference option that is feasible should be done): 1) transfer to another active study site that is open, 2) home visit, 3) telemedicine visit (e.g., by telephone or web conference), and 4) local laboratory visit. These mitigating options only apply in the setting of a public health emergency in which a protocol-specified clinic visit cannot occur and should not be pursued solely due to participant's preference. If the participant does not participate in one of these options, a Safety Telephone call must be conducted within 14 days of the last dosing visit.

Details on which visits and procedures are eligible to be performed at alternative medical facilities will be provided by the Sponsor in writing. All procedures performed at alternative medical facilities will need to be performed as described in this protocol and medical staff will need to be trained accordingly. If a participant cannot attend the study site visit for administration of study drug, a home visit or a visit to an alternative medical facility may be appropriate. Study treatment administration outside of the study site may require appropriately delegated study site staff or a home healthcare service with Sponsor approval.

The Sponsor will determine appropriate start and end dates for each contingency measure, where the duration of the mitigations may begin at the onset of site restrictions for a specific site and/or country and may end once those restrictions are lifted and in accordance with local laws and regulations. The adaptations to the visits and procedures described are alternatives or deviations to the main protocol procedures.

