2.2.5. Changes to Study Execution Following Announcement of Study Termination

1) On 31 January 2024, it was announced that as the study is early terminated, participants enrolled in the study may continue receiving treatment until 01 May 2024. Screening and enrollment would be closed for the study. The participant and care partner, as applicable, should return to the site for a safety follow-up visit 30 days after their last dose. On 16 February 2024, Biogen released a document 221AD305 ENVISION Clarification Letter_16FEB2024_Final Signed, which updated the changes to study execution: Early Termination Visit: assessments and timing (Protocol Section 1.3, Table 2)

Due to the early termination of the study, all participants will be asked to complete this early termination (ET) visit, which, to reduce participant burden, will be limited to assessments related

to participant safety. These assessments are reported in Table 1. Participants should complete this ET visit within 30 days of their last dose of study treatment.

2) Follow-up/End of Study (FU/EOS) Visit: assessments and timing (Protocol Section 1.3, Table 2)

Due to the early termination of the study, all participants are asked to complete their Follow-up/End of Study visit (also referred to as the safety follow-up visit) at 12 weeks (+/- 3 days) after the participant's last dose of study treatment. Participants who wish to withdraw and not receive additional dosing through 01 May 2024 are still encouraged to have a safety follow-up visit 12 weeks from their last dose of study treatment. In addition, similar to the ET visit, the number of assessments that need to be completed is now reduced to lessen participant burden. These assessments are reported below in Table 1. If a participant has had their last dose of study treatment and it has been more than 12 weeks since their last dose and the participant has not had their safety follow-up, then they should complete a safety follow-up visit within 30 days, as defined in Table 1.

3) Substudies (Protocol Section 5.1)

Due to the early termination of the study, all the longitudinal substudies are terminated and samples will no longer be collected for amyloid PET, tau PET, at Weeks 52, 78, and 104/ET.

4) Management of participants who had already discontinued treatment and who were following the visit schedule defined in Table 3 (Protocol Section 1.3, Table 3)

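### The 14-day safety call in Protocol 11.4.1 is timed from the last dosing visit, so its limit expires before a lost follow-up visit, or nearly any lost off-treatment visit, is due

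*Protocol*

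**What the plan says.** Protocol 11.4.1 applies whenever a scheduled clinic visit cannot take place because of a public health emergency. It lists four alternatives in order of preference: another site, a home visit, a telemedicine visit, and a local laboratory visit. If the participant takes none of them, "a Safety Telephone call must be conducted within 14 days of the last dosing visit". The section does not define the last dosing visit, and it does not say whether the call repeats when further visits are lost.

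Two groups of visits fall well after dosing:

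- **Safety follow-up.** Participants who stop treatment early are to "attend a safety FU Visit 18 weeks after the last dose of study treatment" (Protocol 8.1). Completers attend at Week 122, also 18 weeks after the last dose (Protocol 5.2). After the study was terminated, the visit was moved to a point "at 12 weeks (+/- 3 days) after the participant's last dose of study treatment" (SAP 2.2.5).
- **Off-treatment visits.** "Participants who discontinue treatment but agree to stay in the study will follow the abbreviated visit schedule outlined here" (Protocol 1.3, Table 3, footnote 1). Table 3 has no infusion row.

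Other provisions also bear on the point:

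- Adverse event reporting is "Monitor and record continuously throughout the study" in Table 3.
- Protocol 5.2 schedules "Eight telephone safety FU contacts after each of the first 8 doses". Table 1 places these calls at Weeks 2 to 30, and its footnote 24 says that "Safety FU telephone contacts occur during dose escalation".
- Protocol 8.2 requires sites to try to contact a participant who misses a visit and to rebook it.
- Protocol 10 lets the Sponsor allow remote safety assessments.

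**The concern.** A fallback call stands in for a lost visit, so its time limit should run from that visit. Here the limit runs from a dosing visit, while the trigger is any scheduled visit. When the lost visit lies far from the last dose, the site either finds that the limit has expired or, if warned early, can comply only with a call made weeks or months before the visit was due. Such a call cannot cover the interval that the visit was meant to cover.

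The affected visits have a safety purpose. SAP Table 1, footnote 2, describes the follow-up visit as monitoring after washout. Table 3 participants include those who stopped for severe ARIA-H, ARIA with serious symptoms, or a cerebral hemorrhage larger than 1 cm (Protocol 5.3.1.4 and 8.1). What is at stake is the completeness of safety contact in a rare situation, not the efficacy inference.

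**Working it through.** **Inputs**

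- Limit: 14 days from the last dosing visit (Protocol 11.4.1).
- Dosing: Day 1, then every 4 weeks to Week 104, 27 visits in all (Protocol 5.2). Doses are to be at least 21 days apart (Protocol 7.2).
- Follow-up: 18 weeks after the last dose, later 12 weeks ± 3 days (SAP 2.2.5).
- Table 3 nominal days: 85, 169, 281, 351 (the Week 50/52 column), 449, 547, 617, 729 and 743. The ET visit has no fixed day and is left out.

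**Formulas**

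- Study day = 7 × week + 1. Week 104 gives Day 729 and Week 122 gives Day 855, as printed in Table 2.
- Days by which the limit precedes a visit = visit day − (last dose day + 14).

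**Safety follow-up visit**

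- Week 122: 855 − (729 + 14) = 112 days. With ± 3 days at both visits, the range is 106 to 118.
- Revised visit: 84 − 14 = 70 days. With ± 3 days, the range is 67 to 73.

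**Table 3: first visit after each possible last dose before Week 104**

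| Last dose (week) | First Table 3 visit | Days by which the limit precedes it |
|---|---|---|
| 0, 4, 8 | Week 12 | 70, 42, 14 |
| 12, 16, 20 | Week 24 | 70, 42, 14 |
| 24, 28, 32, 36 | Week 40 | 98, 70, 42, 14 |
| 40, 44, 48 | Week 50 | 56, 28, 0 |
| 52, 56, 60 | Week 64 | 70, 42, 14 |
| 64, 68, 72, 76 | Week 78 | 84, 56, 28, 0 |
| 80, 84 | Week 88 | 42, 14 |
| 88, 92, 96, 100 | Week 104 | 98, 70, 42, 14 |

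Of the 26 last doses, 24 give a positive number (14 to 98 days). Two give zero (Weeks 48 and 76), where the limit falls on the nominal day of the visit.

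**All later Table 3 visits**

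- The eight rows leave 9, 8, 7, 6, 5, 4, 3 and 2 later visits per last dose: 27 + 24 + 28 + 18 + 15 + 16 + 6 + 8 = 142 combinations.
- The limit has passed in 140 and falls on the day in 2. If Weeks 50 and 52 count as separate visits, it has passed in 153 of 155.
- Example: the last dose is at Week 20 (Day 141), so the limit is Day 155. That is 169 − 155 = 14 days before Week 24 and 547 − 155 = 392 days before Week 78.

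**Lost dosing visits**

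- If the last dosing visit means the last one held, the limit passed 28 − 14 = 14 days before the lost visit was due, or 21 − 14 = 7 days at the minimum gap.
- If it means the last one scheduled, the limit falls 14 days after the lost visit and the rule works.
- Of the 26 dosing visits after Day 1, 7 (Weeks 4 to 28) have a Table 1 call two weeks later, which leaves 19 (Weeks 32 to 104). Protocol 5.2 ties those calls to doses given and Table 1 ties them to study weeks, so even these 7 are not certain.

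**On-treatment visits without dosing** (Weeks 14, 22, 26, 30, 42, 50, 78 and 106). Each is nominally 14 days after the preceding scheduled dose, so if that dose was given the limit falls on the day the visit is due.

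**The case against.** The strongest reply is that the sentence was meant as a post-dose check. The routine calls in Table 1 fall 14 days after each of the first eight doses, and the limit in 11.4.1 copies that interval. On this reading, the call was never meant to replace a follow-up or Table 3 visit, and other provisions cover those. Section 8.2 makes contact after a missed visit mandatory, adverse events are recorded throughout, and Section 10 allows remote safety visits under a Study Reference Manual that is not among the documents. Section 11.4.1 also says that contingency measures start only on written notice from the Sponsor, with details in clarification letters. Finally, anyone affected has already passed over four options, one of which can be a telephone visit.

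Much of this stands, and it is why the effect is small. It does not correct the rule:

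- The trigger covers every scheduled visit, so a narrower intent cannot be read from the text.
- Section 8.2 sets no safety content, and Section 10 is at the Sponsor's discretion.
- Tables 2 and 3 as shown list no routine calls, so those calls do not reach the follow-up visit or Table 3 participants.
- The Sponsor's letters could re-time the call, but nothing says that they will.

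It is also fair to say that the Table 3 counts restate one fact: people off treatment have no later dosing visit. The counts show reach, not frequency. They assume that the last dose marks discontinuation. If discontinuation is recorded later, the first Table 3 visit can only be the same one or a later one, so the gap does not shrink.

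**Conclusion.** The rule is wrong as written, at the lowest level of importance. For the safety follow-up visit and for Table 3 visits, neither reading of the last dosing visit rescues it. The limit expires 112 days before the 18-week follow-up (70 days before the 12-week one), and before 140 of 142 combinations of last dose and later Table 3 visit. For lost 4-weekly dosing visits there is an ambiguity rather than an error.

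These figures rest on nominal visit days. The documents give no basis for estimating how many participants would be affected, but the number is likely to be very small, because each must lose a visit to a public health emergency and take none of the alternatives. There is no effect on endpoints, alpha or power. Since the study was terminated early, the point now matters mainly for the accuracy of the procedure and for any reuse of the text.

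**What to change.** Replace the sentence in 11.4.1 with wording of this kind: if the participant takes up none of these options, the site makes a safety telephone call within 14 days after the scheduled date of the visit that could not take place; this applies to each such visit, including Table 3 visits and the safety follow-up visit.

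For a lost Week 122 visit the call would be due by Day 855 + 14 = 869. For a lost 12-week follow-up it would be due by day 84 + 14 = 98 after the last dose. The clinical team should confirm the 14-day interval. If a post-dose check is also wanted, state it as a separate requirement.

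The cost is one sentence and a call for each lost visit, of a kind the plan already intends.

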#### 11.4.2. Pregnancy

Participants should not become pregnant during the study and for 24 weeks after their last dose of study treatment. If a female participant becomes pregnant, study treatment must be discontinued *immediately*.

The Investigator must report a pregnancy occurring in a female participant from first dose of study drug to 24 weeks after her last dose by faxing or emailing the appropriate form to the Sponsor within 24 hours of the study site staff's becoming aware of the pregnancy. Refer to the Official Study Contact List in the Study Reference Manual for complete contact information. The Investigator or site staff must report the outcome of the pregnancy to the Sponsor. A pregnancy is not considered an AE and should not be recorded on the AE CRF.

Congenital abnormalities and birth defects in the offspring of male or female participants should be reported as an SAE if conception occurred during the study treatment period or within 24 weeks after last dose of study treatment.

#### 11.4.3. Overdose

An overdose is any dose of study treatment administered to a participant that exceeds the dose assigned to the participant according to the protocol. Overdoses are not considered AEs and should not be recorded as an AE on the CRF; however, all overdoses must be recorded on an Overdose form and faxed or emailed to the Sponsor within 24 hours of the site staff becoming aware of the overdose. An overdose must be reported to the Sponsor even if the overdose does not result in an AE. If an overdose results in an AE, the AE must be recorded. If an overdose results in an SAE, both the SAE and overdose forms must be completed and faxed or emailed to the Sponsor. All study treatment-related dosing information must be recorded on the dosing CRF.

